4.2.1 Inclusion Criteria

1. Male or female age 18 years or older.
2. Refractory or relapsed lymphoma (per WHO Classification system) defined as:
 - Non-Hodgkin lymphoma (NHL): Patients with histologically confirmed NHL (including stage \geq Ib cutaneous T-cell lymphoma [CTCL]) who have failed or are intolerant to any established therapy known to provide clinical benefit at current state of disease. There is no upper limit to the number of prior therapies.
 - Hodgkin lymphoma: Patients with histologically confirmed classical Hodgkin lymphoma who have failed or are intolerant to brentuximab vedotin. Patients must have received a checkpoint inhibitor. There is no upper limit to the number of prior therapies.
3. Pathologically confirmed relapsed or refractory lymphoma; a biopsy at any relapse is acceptable.
4. Availability of formalin-fixed paraffin-embedded (FFPE) tumor tissue block. An FFPE block from a current biopsy is preferred; however, archival tissue taken at any prior relapse is acceptable. If tissue block is not available, slides from a FFPE block may be acceptable for eligibility upon consultation with the Sponsor.
5. Measurable disease, defined by the 2014 Lugano Classification Criteria (including CTCL patients without evidence of skin disease) ([Appendix 13.2](#)). CTCL patients with skin disease and modified Severity-Weighted Assessment Tool (mSWAT) criteria >0 , or absolute Sézary count ≥ 1000 cells/ μ L are eligible ([Appendix 13.3](#)).
6. ECOG performance status 0 to 2.
7. Absolute neutrophil count (ANC) ≥ 1500 / μ L. Criterion not applicable to adult T cell leukemia/lymphoma (ATLL) patients.
8. Platelet count of ≥ 75000 / μ L. Criterion not applicable to ATLL patients.
9. Hemoglobin ≥ 9.0 g/dL without transfusion within the 2 weeks prior to Day 1. Criterion not applicable to ATLL patients.
10. Serum/plasma creatinine ≤ 1.5 mg/dL, or if the patient has a creatinine > 1.5 mg/dL, a measured creatinine clearance must be > 80 mL/min as calculated by the Cockcroft and Gault equation.⁴

11. Serum/plasma alkaline phosphatase, alanine aminotransferase, and aspartate aminotransferase ≤ 2 times the upper limit of normal (ULN); ≤ 5 times ULN if there is liver or bone involvement.
12. Total serum/plasma bilirubin ≤ 1.5 times ULN (patients with known Gilbert's syndrome may have a total bilirubin up to ≤ 3 times ULN).
13. Women of childbearing potential must have a negative blood beta-human chorionic gonadotropin (β -HCG) pregnancy test within 7 days prior to Day 1.
14. Women of childbearing potential* must agree to use a highly effective** method of contraception from the time of giving informed consent until at least 16 weeks after the last dose of ADCT-301. Men with female partners who are of childbearing potential must agree that they or their partners will use a highly effective method of contraception from the time of giving informed consent until at least 16 weeks after the patient receives his last dose of ADCT-301.

*Defined as: Sexually mature women who have not undergone bilateral tubal ligation, bilateral oophorectomy, or hysterectomy; or who have not been postmenopausal (i.e., who have not menstruated at all) for at least 1 year.

Defined as: Hormonal contraceptives (oral, injectable, patch, intrauterine devices), male partner sterilization, or total abstinence from heterosexual intercourse, when this is the preferred and usual lifestyle of the patient. **Note: The double-barrier method (e.g., synthetic condoms, diaphragm, or cervical cap with spermicidal foam, cream, or gel), periodic abstinence (such as calendar, symptothermal, post-ovulation), withdrawal (coitus interruptus), lactational amenorrhea method, and spermicide-only are not acceptable as highly effective methods of contraception.

4.2.2 Exclusion Criteria

1. Patients who have an option for any treatment with proven clinical benefit for their lymphoid malignancy at current state of disease.
2. Active graft-versus-host disease.
3. Autologous or allogenic transplant within the 60 days prior to Cycle 1 Day 1
4. Evidence of myelodysplasia or myeloid leukemia by morphology, immunostains, flow cytometry, or cytogenetics on a bone marrow aspirate or biopsy.
5. Known history of positive serum human ADA or known allergy to any component of ADCT-301.
6. History of symptomatic autoimmune disease (e.g., rheumatoid arthritis, systemic progressive sclerosis [scleroderma], systemic lupus erythematosus, Sjögren's syndrome, autoimmune vasculitis [e.g., Wegener's granulomatosis]);

7. History of neuropathy considered of autoimmune origin (e.g., polyradiculopathy including Guillain-Barré syndrome and myasthenia gravis); other central nervous system autoimmune disease (e.g., poliomyelitis, multiple sclerosis).
8. History of recent infection (within 4 weeks of C1D1) considered to be caused by one of the pathogens listed in [Section 7.3.4.5](#): HSV1, HSV2, VZV, EBV, CMV, measles, Influenza A, Zika virus, Chikungunya virus, mycoplasma pneumonia, Campylobacter jejuni, or enterovirus D68.
9. Known seropositive for human immunodeficiency virus (HIV), hepatitis B surface antigen (HbsAg), or antibody to hepatitis C virus (anti-HCV) with confirmatory testing and requiring anti-viral therapy. **Note:** testing is not mandatory to be eligible. If patient is at risk for having undiagnosed HCV (e.g., history of injection drug use), HCV testing should be considered.
10. History of Steven's Johnson's syndrome or toxic epidermal necrolysis syndrome.
11. Pregnant or breastfeeding women.
12. Significant medical comorbidities, including uncontrolled hypertension (diastolic blood pressure > 115 mm Hg), unstable angina, congestive heart failure (greater than New York Heart Association class II), severe uncontrolled ventricular arrhythmias, or electrocardiographic evidence of acute ischemia, poorly controlled diabetes, severe chronic pulmonary disease, coronary angioplasty, or myocardial infarction within 6 months prior to screening, or uncontrolled atrial or ventricular cardiac arrhythmias.
13. Use of any other experimental medication(s) within 14 days or 5 half-lives, but in no case < 14 days prior to the start of study treatment on Cycle 1, Day 1, except if approved by the Sponsor.
14. Major surgery, radiotherapy, chemotherapy, or other anti-neoplastic therapy (including prednisone \geq 40 mg/day or equivalent) within 14 days or 5 half-lives (whichever is shorter) prior to Cycle 1, Day 1 treatment, except if approved by the Sponsor.
15. Failure to recover (to Common Terminology Criteria for Adverse Events [CTCAE Version 4.0] Grade 0 or Grade 1) from acute non-hematologic toxicity (except all grades of alopecia or Grade 2 or lower neuropathy), due to previous therapy, prior to Screening.
16. Congenital long QT syndrome or a corrected QTc interval \geq 450 ms at screening (unless secondary to pacemaker or bundle branch block).
17. Active second primary malignancy other than non-melanoma skin cancers, nonmetastatic prostate cancer, in situ cervical cancer, ductal or lobular carcinoma in situ of the breast, or other malignancy that Sponsor Medical Monitor and Investigator agree, and document should not be exclusionary.

- 18.** Any other significant medical illness, abnormality, or condition that would, in the Investigator's judgment, make the patient inappropriate for study participation or put the patient at risk.

5 Study Procedures

5.1 Procedures by Study Day

The following procedures will be performed during the study.

5.1.1 Screening Period (Day –28 to –1)

The following procedures will be performed within 28 days prior to Day 1:

- Signed and dated Institutional Review Board (IRB) /Independent Ethics Committee (IEC) approved informed consent form (ICF) obtained prior to performing any study evaluations. Results (e.g., from laboratory tests or radiographic evaluations, etc.) obtained prior to the date of informed consent but within the allowed timeframe for screening may be used for determination of patient eligibility only if obtained as part of the patient's standard of care.
- Demography.
- Medical history (to include a complete history of all surgeries and significant diagnoses and all cancer treatment [including surgery, radiation therapy, chemotherapy, etc.]) and assessment of cardiac risk factors (e.g., history of angina pectoris, coronary artery disease or cerebrovascular accident, transient ischemic attack, cardiac failure with known ejection fraction < 40%, or cardiac arrhythmia requiring medical therapy).
- Pregnancy test (serum or urine, women of childbearing potential only).
- 
- Physical examination, including neurological examination and including whole body skin assessment. Whole body skin assessment does not have to be performed by a dermatologist; however, any unexplained lesion will be referred to a dermatologist for further evaluation and skin biopsy, if clinically warranted. The examination must include a determination if the patient has had any infection. At the discretion of the investigator, evaluation of any reported infection must be conducted to rule out infection with a microorganism that may be associated with autoimmune or neurological disease(s) as specified in the exclusion criteria.
 - Neurological assessment (as part of the physical examination) including strength, sensation, and deep-tendon reflexes throughout; examination does not need to be conducted by neurologist unless there are abnormal findings not explained by previous medical history (e.g., a patient with left sided weakness known to be a result of a previous CVA would not need to see a neurologist as part of this study)

and that could be linked to or may be an early indicator of polyradiculopathy/GBS, such as ascending (bilateral) sensory loss or motor weakness.

- Vital sign measurements.
- Height.
- Weight.
- Eastern Cooperative Oncology Group (ECOG) performance status.
- Disease assessments: Assessed using positron emission tomography - computed tomography (PET-CT) and diagnostic CT of the neck/chest/abdomen/pelvis and other areas of known disease or newly suspected disease with a clinical examination for lymphoma. Contrast should be used unless contraindicated. Magnetic resonance imaging (MRI) is permitted if diagnostic CT is contraindicated. The same assessments methods used at Screening which identify sites of disease should be used uniformly for all subsequent assessments.

Note: PET-CT is only required at screening for ^{18}F -fluorodeoxyglucose (FDG) avid, nodal lymphomas (defined as per the Lugano Classification criteria as essentially all eligible histologies except small lymphocytic lymphoma, lymphoplasmacytic lymphoma/Waldenstrom's macroglobulinemia, mycosis fungoides, and marginal zone NHLs, unless there is a suspicion of aggressive transformation). If PET-CT examination is negative at Screening, subsequent PET-CT is not required. If PET-CT is positive, subsequent diagnostic CT and MRI are not needed, unless clinically indicated.

- Hematology.
- Coagulation panel.
- Biochemistry.
- Urinalysis.
- 12-lead electrocardiogram (ECG).
- AEs.
- Concomitant medication use (including prescription or over-the-counter medication, herbal or naturopathic products) within the 14 days prior to Day 1.

5.1.2 Day 1 (\pm 3 days) of Each Cycle

Day 1 of each cycle occurs on infusion day. The following procedures will be performed prior to ADCT-301 infusion unless otherwise specified:

- Serum or urine pregnancy test (women of childbearing potential, Cycle 1 only) is not required if screening pregnancy test was performed using serum and was done < 7 days before dosing with negative result.
- Physical examination, including neurological examination and including whole body skin assessment, unless a physical examination was performed within 3 days prior to Day 1. The examination must include a determination if the patient has had any infection. At the discretion of the investigator, evaluation of any reported infection must be conducted to rule out infection with a microorganism that may be associated with autoimmune or neurological disease(s) as specified in the exclusion criteria.
- On Day 1 of Cycle 1, vital signs (arterial blood pressure, heart rate, respiratory rate, temperature) are measured before the start of the infusion, every 30 minutes during the infusion, and at the end of infusion. If no clinically significant changes occur during the first infusion, measurements are required prior to infusion start, hourly during infusion, and end of infusion for all subsequent infusions. For Cycles 1 and 2, patients will be monitored for 4 hours post-infusion with vital signs being measured 1 hour after the end of infusion and at discharge.

Note: Timing of measurements is \pm approximately 5 minutes.

- Weight, unless an assessment was performed within 3 days prior to Day 1.
- ECOG performance status, unless an assessment was performed within 3 days prior to Day 1.
- Disease assessments:
 - To be performed within 6 days prior to Day 1 of Cycles 3 and 5 and thereafter every third cycle (i.e., Cycles 8, 11, 14, etc.), until disease progression or more frequently, if clinically indicated.
 - The same methods used at Screening which identify sites of disease should be used uniformly for all subsequent assessments.

Note: The results of the disease assessment are to be available to the Investigator prior to administration of study drug.

Note: if PET-CT examination is negative at Screening, subsequent PET-CT is not required. For CTCL patients with disease limited to the skin, disease assessments after screening will be performed using mSWAT; radiological imaging after screening for CTCL patients with disease limited to the skin is not required unless clinically indicated.

- Hematology, coagulation panel, and biochemistry parameters will be measured prior to dosing unless the last sample was collected:
 - <24 hours before the start of ADCT 301 infusion on Day 1 of Cycle 1, or
 - <72 hours before the start of ADCT-301 infusion on Day 1 of Cycle 2 and subsequent cycles.
- Urinalysis and sample collection for additional renal function studies will be done prior to dosing unless the last sample was collected:
 - <24 hours before the start of ADCT 301 infusion on Day 1 of Cycle 1, or
 - <72 hours before the start of ADCT-301 infusion on Day 1 of Cycle 2 and subsequent cycles.
- 12-lead ECG (see [Section 7.3.5](#) for timing of serial ECG measurements).
- Sample collection for central laboratory assessment of PK, ██████████, ADA, (for additional sample collections following dosing, see [Appendix 13.1.2](#)).
- Sample collection and shipment for PBMC subset analysis (Cycles 1 and 2, for additional sample collections following dosing see [Appendix 13.1.2](#); only in Study Part 2).
- Sample collection for ██████████, Cycles 1 and 2.
- Sample collection for ██████████, Cycles 1 and 3.
- AEs.
- Concomitant medication use.
- Premedication administration, if applicable ([Section 6.2](#)).
- ADCT-301 administration.

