6.1 Method of Assigning Patients to Treatment Groups

This is an open-label study that will be conducted in 2 parts. In both parts, ADCT-301 will be administered on Day 1 of each cycle. The duration of each cycle will be 21 days (3 weeks).

In Part 1, dose escalation will begin with the 3 µg/kg dose starting dose (Dose Level 1). The maximum dose will be 300 µg/kg. Patients will be assigned to the appropriate dose level according to the CRM design ([Section 13.5](#)) and judgment of the DESC.

In expansion (Part 2), all patients will be assigned to the dose level of ADCT-301 as identified in Part 1 by the DESC.

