7.1 Efficacy Assessments

Disease assessments will occur every other cycle for the first 2 evaluations (6 weeks [end of Cycle 2 \pm 1 week] and 12 weeks [end of Cycle 4 \pm 1 week]), and every third cycle (every 9 weeks [e.g., end of Cycles 7, 10, 13, etc., \pm 1 week]) thereafter until progression or more frequently, if clinically indicated. Assessments may be performed within \pm 1 week of the required timepoint and response assessment must be available prior to initiation of dosing at the subsequent cycle.

In case of dose delays, disease assessment should be maintained at the frequencies defined above and response assessment is required prior to resumption of ADCT-301 dosing (only if the interval from last scan is \geq 6/9 weeks, as applicable) to rule out disease progression.

Tumor response will be determined by the Investigator, based on the 2014 Lugano Classification Criteria ([Appendix 13.2](#)) and Global Response Score Grading Scales for CTCL ([Appendix 13.3](#)). Images will be obtained according to local site imaging requirements. Images will be required to be submitted for a central/independent review for Part 2. Submission instructions for the central/independent review will be provided in a separate manual.

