- 8 Screening tumor assessments: PET-CT and diagnostic CT of the neck/chest/abdomen/pelvis and other areas of known disease or newly suspected disease with a clinical examination for lymphoma. Contrast should be used unless contraindicated. Magnetic resonance imaging (MRI) is permitted if diagnostic CT is contraindicated. The same assessment methods used at Screening should be used for all subsequent assessments. Note: PET-CT is only required at screening for FDG-avid, nodal lymphomas (defined as per the Lugano Classification criteria as essentially all eligible histologies except small lymphocytic lymphoma, lymphoplasmacytic lymphoma/Waldenstrom's macroglobulinemia, mycosis fungoides, and marginal zone NHLs, unless there is a suspicion of aggressive transformation. If PET-CT examination is negative at Screening, subsequent PET-CT is not required. If PET-CT is positive, subsequent diagnostic CT and MRI are not needed, unless clinically indicated. In case of dose delays, response assessment is required prior to resumption of ADCT-301 dosing (only if the interval from last scan is \geq 6/9 weeks, as applicable) to rule out disease progression. For CTCL patients with disease limited to the skin, disease assessments after screening will be performed using mSWAT; radiological imaging after screening for CTCL patients with disease limited to the skin is not required unless clinically indicated.
- 9 Disease assessments will be performed within 6 days prior to Day 1 of Cycles 3 and 5 and thereafter every third cycle (i.e., Cycles 8, 11, 14, etc.) until disease progression or more frequently, if clinically indicated. The same assessment methods used at Screening which identify sites of disease should be used uniformly for all subsequent assessments
- 10 Patients who already have documented objective disease progression do not need to have assessments repeated. Patients who do not already have documented objective disease progression will have assessments performed if the most recent disease assessment was greater than 9 weeks prior to the end of treatment visit.

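### Scans are tied to the infusion day in Section 5.1.2 and schedule footnote 9 but held to a stated frequency under dose delay in Section 7.1, so some delay patterns move the progression scan by up to the length of the delay

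*Protocol*

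**What the plan says.** Three parts of the protocol set the scan times.

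- **Section 5.1.2** says of disease assessments: "To be performed within 6 days prior to Day 1 of Cycles 3 and 5 and thereafter every third cycle" (Cycles 8, 11, 14 and so on). It also states that "Day 1 of each cycle occurs on infusion day", so the anchor moves with the dose. It has no rule for delayed doses.
- **Section 13.1.1, footnote 9** uses the same anchor: "Disease assessments will be performed within 6 days prior to Day 1 of Cycles 3 and 5 and thereafter every third cycle". Footnote 8, on the same row, adds: "In case of dose delays, response assessment is required prior to resumption of ADCT-301 dosing". This applies only when the last scan is at least 6 or 9 weeks old.
- **Section 7.1** opens with "Disease assessments will occur every other cycle for the first 2 evaluations (6 weeks [end of Cycle 2" and goes on to week 12 and then every 9 weeks, each with a window of 1 week either side. It adds: "In case of dose delays, disease assessment should be maintained at the frequencies defined above", followed by the same check before resumption. It also requires that "response assessment must be available prior to initiation of dosing at the subsequent cycle".

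Section 6.4 allows a suspension of up to 21 days, and longer in consultation with the sponsor. SAP Sections 4.9.2 and 4.9.4 display DOR and PFS by dose level with Kaplan-Meier methods. They give no rule for assessments made off schedule. SAP Section 4 rules out hypothesis testing.

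**The concern.** A site working from Section 5.1.2 or footnote 9 lets the scan slip with the infusion. A site working from Section 7.1, read in weeks, does not. Footnote 8 carries only half of Section 7.1's delay rule: it has the check before resumption but not the instruction to hold the frequency.

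Progression is dated from the scan that shows it, so a later scan gives a longer PFS. DOR is lengthened too where the scan that slips is the one showing progression. Section 6.4 links delays to toxicity. If toxicity, and so delay, rises with dose, the shift would be larger at the higher dose levels, which are the ones being compared descriptively. The recorded times would also depend on which section a site follows.

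**Working it through.** **Inputs.** Cycle length is 21 days (Section 6.1). Day 1 is the infusion day (5.1.2). Scan cycles are 3, 5, 8 and so on (5.1.2, footnote 9). Calendar times are weeks 6 and 12, then every 9 weeks, plus or minus 1 week (7.1). Scan before resumption if the last is at least 6/9 weeks old (7.1, footnote 8). Delay is up to 21 days per suspension (6.4).

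**Formula.** Counting days from Cycle 1 Day 1, Day 1 of cycle c falls on day 21 × (c − 1) + cumulative delay.

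**Step 1: no delay.** Cycle 3: 21 × 2 = 42. Cycle 5: 21 × 4 = 84. Cycle 8: 21 × 7 = 147. These are weeks 6, 12 and 21 (12 + 9), so Section 7.1's own figures are reproduced and the rules agree.

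**Step 2: cycle anchor alone.** The lag equals the cumulative delay d. For the first scan, 5.1.2 allows days 36 + d to 42 + d, and 7.1 allows days 35 to 49.
- d up to 7: always inside (42 + 7 = 49).
- d of 8 to 13: depends on the scan day.
- d of 14 or more: always outside (36 + 14 = 50).

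**Step 3: add the check before resumption.** Assumptions: screening scan 7 days before Cycle 1 Day 1, scans placed on Day 1, a 6-week limit through Cycle 5 and 9 weeks after that.

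| Delay | Scan days, cycle anchor alone | Effect of footnote 8 |
|---|---|---|
| 21 days at Cycle 2 | 63, 105, 168 | Extra scan on day 42; first assessment on time |
| 21 days at Cycle 4 | 42, 105, 168 | Extra scan on day 84 |
| 21 days at Cycle 7 | 42, 84, 168 | Extra scan on day 147 |
| 21 days at Cycle 3 | 63, 105, 168 | None |
| 21 days at Cycle 5 | 42, 105, 168 | None |
| 21 days at Cycle 6 or 8 | 42, 84, 168 | None |
| 7 days at each of Cycles 2 to 5 | 56, 112, 175 | None |

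The Cycle 3 delay is not rescued because the check applies at resumption, on day 63, when footnote 9 already calls for the scan.

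**Step 4: average lag.** Over all 256 combinations of 0, 7, 14 or 21 days at Cycles 2 to 5, with progression uniform over days 1 to 84, the mean extra detection time in days is:

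| Total delay (days) | 7 | 21 | 42 | 63 | 84 |
|---|---|---|---|---|---|
| Cycle anchor alone | 3.5 | 9.8 | 16.7 | 20.3 | 21.0 |
| Footnotes 8 and 9 | 3.5 | 7.3 | 7.8 | 3.7 | 0 |

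**Step 5: effect on PFS.** Simulation assumptions: exponential progression with a true median of 5 weeks, detection at scans only, 40% of cycles delayed by 1, 2 or 3 whole weeks, screening scan 1 to 3 weeks before Cycle 1.
- Calendar scans: mean PFS 11.0 weeks.
- Footnotes 8 and 9: 11.2 to 11.4 weeks, a shift of 0.2 to 0.4.
- Cycle anchor alone: about 12.1 weeks, a shift of about 1.1.

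If delays are instead spread evenly over 1 to 3 weeks, the mean with footnotes 8 and 9 is 11.3 to 11.7 weeks, a shift of 0.3 to 0.7.

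**The case against.** **Footnote 8 binds any site that follows the schedule.** This stands and limits the point. A reader might infer that detection gets later the more delays a patient has, or that 21-day delays at both Cycles 2 and 3 push the first scan to week 12. The documents do not support either. In the second case Cycle 2 resumes on day 42, the screening scan is by then at least 6 weeks old, and a scan is required that day. Step 4 shows the average lag under both footnotes peaking at about 8 days and then falling to zero.

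**The calendar anchor is an inference.** Section 7.1 states its frequency in cycles as well as weeks. That is so. But the delay sentence does little unless the frequency is held while cycles slip, and the 6/9-week test is in weeks. If Section 7.1 is ambiguous, that is a further reason to settle on one anchor.

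**Detection at scans only overstates the effect.** This also stands. The SAP counts clinical progression at end of treatment or study, and death, as PFS and DOR events, and the protocol allows extra scans when clinically indicated. A large shift in the median would be a fragile argument too: with a true median of 8 weeks, the observed median is 12.0 weeks on calendar and cycle-anchored scans alike.

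**The windows need not clash.** A reader might infer that they are incompatible. Without delay, a scan in the 6 days before Day 1 (days 36 to 42) meets both sections. What remains is that the last days of Section 7.1's window (days +4 to +7) cannot be used with the result in hand and the next dose still within 3 days of plan.

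**Nothing is tested.** PFS and DOR are secondary and descriptive, and no sample size or dose-escalation rule depends on them.

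**Conclusion.** The inconsistency is real and minor. Under the cycle anchor, some delay patterns move a scan by up to the length of the delay, and footnote 8 repairs only some of them. The clearest unrepaired case is 21 days at Cycle 3, which puts the first scan on day 63, two weeks past the end of Section 7.1's window (63 − 49 = 14 days).

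The likely effect on mean PFS is a fraction of a week if footnote 8 is followed, and about 1 week if a site uses Section 5.1.2 or footnote 9 alone. Both figures assume 40% of cycles delayed and a short true median, and both are upper-side because they ignore clinical progression and death. The documents give no delay rates, overall or by dose, so a bias that differs between dose levels is possible but not established.

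**What to change.** Reconcile Sections 5.1.2 and 7.1 and footnotes 8 and 9 to one calendar anchor: weeks 6 and 12 from Cycle 1 Day 1, then every 9 weeks, regardless of dose delays. Give one window in all of these places, ending before the next infusion, so that the result can be available as the protocol already requires. Keep the existing check before dosing resumes.

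The cost is a wording change, and the Section 7.1 schedule read in weeks gains no scans. A patient with a delayed dose may need a separate scan visit, and sometimes an additional scan under the check before resumption.
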